13.5. Disposition, Demographics, and Baseline Characteristics

The number and percentage of patients completing the study through Week 48 (ie, completers) or prematurely discontinuing before Week 48 will be summarized. Disposition will also be summarized over the entire 96-week duration of the study. Reasons for premature discontinuation will also be summarized.

Demographic characteristics including age (years), race, ethnicity, and baseline characteristics including height/length (cm), and weight (kg) will be summarized by age cohort and overall. Demographic data and baseline characteristics will be presented in data listings.

13.6. Medical History

Medical history will be presented in data listings.

13.7. Dosing and Compliance

The cumulative exposure to eteplirsen, total volume of drug administered (mL), total number of infusions received, and the cumulative amount of drug received will be summarized by age cohort and overall for all treated patients. Dosing information will be provided in a data listing.

13.8. Safety Analysis

13.8.1. Safety Variables

The safety variables are:

- Incidence of AEs
- Abnormal changes in clinical safety laboratory parameters
- Abnormal changes in vital signs
- Abnormal changes in physical examination findings
- Abnormal changes in ECG and/or ECHO parameters

13.8.2. Safety Analyses

Safety analyses will be descriptive in nature. Summary statistics for each parameter at a specific visit, as well as the change from baseline to that visit, will also be displayed. All safety data will be presented in the data listings.

13.8.2.1. Adverse Events

Only treatment-emergent adverse events (TEAEs) will be summarized by the Medical Dictionary for Regulatory Activities (MedDRA) system organ class (SOC) and preferred term. Non-treatment-emergent events will be recorded in data listings. For all AE tables, the number and percentage of patients reporting AEs will be grouped by MedDRA SOC and preferred term for each age cohort and overall.

Multiple occurrences of the same AE (at the preferred term level) in the same patient will be counted only once in frequency tables. If a patient experiences multiple episodes of the same

event with different severity, the event with the maximum severity will be used to summarize AEs by severity (likewise for relationship). Treatment-related TEAEs will be defined as those that the Investigator considers related to the IP.

The following summary tables will be produced:

- TEAEs
- TEAEs by severity
- Treatment-related TEAEs
- Treatment-related TEAEs by severity
- TEAEs related to study procedures
- TEAEs related to the underlying disease
- SAEs

In addition, all SAEs, regardless of their treatment-emergent status will be summarized.

The following listings will be produced:

- Non-treatment-emergent AEs
- All TEAEs
- AEs leading to discontinuation
- SAEs

13.8.2.2. Physical Examinations, Vital Signs, Height, and Weight

Vital signs, height/length, and weight will be presented by visit for each age cohort and overall, summarizing the actual values and change from baseline to each visit for each parameter using descriptive statistics. Frequency tables of predefined change to abnormal in vital sign values will be generated.

Data obtained from physical examinations will be presented in patient data listings. Any clinically significant findings will be recorded as AEs.

13.8.2.3. Clinical Safety Laboratory Tests

Clinical chemistry, hematology, renal function, coagulation, and urinalysis will be presented by visit for each age cohort and overall, summarizing the actual value and change from baseline to each visit for each parameter using descriptive statistics for each continuous, and frequency tables for each discrete parameter. Frequency tables of predefined change to abnormal of select laboratory parameter values will be generated.

13.8.2.4. Electrocardiograms

The actual value and change from baseline to each visit will be presented by visit for each age cohort and overall, summarizing the actual values and change from baseline to each visit for each parameter using descriptive statistics.

13.8.2.5. Echocardiograms

ECHO parameters, including the LVEF value and change from baseline in LVEF to each visit, will be summarized by visit for each age cohort and overall.

13.8.2.6. Prior and Concomitant Medications and Physiotherapeutic Interventions

All prior medications (including prior DMD medication) and concomitant medications, as well as physiotherapeutic interventions, will be presented in data listings.

13.10. Pharmacokinetic Analysis

Results of all PK analyses will be provided as a separate PK report which will be appended to the final CSR and summarized in the CSR.

Pharmacokinetic parameters of eteplirsen will be determined from plasma and urine concentration data. Individual plasma and urine levels of eteplirsen will be listed with the corresponding time relative to eteplirsen administration, and summary statistics will be generated by per-protocol time of collection. PK parameters for eteplirsen will be calculated using non-compartmental analysis and/or using population PK methodology, as appropriate. Actual sampling times will be used in all final PK analyses; per-protocol times will be used to calculate mean plasma concentrations for graphical displays.

Plasma and urine concentrations will be listed. PK parameters in plasma and urine will be summarized by dose level and age cohort. Plasma concentrations will be plotted versus elapsed time for dose level means and for individual patients. Dose proportionality will be evaluated across the range of doses studied.

13.11. Interim Analysis

An interim analysis of the PK and safety data following completion of dose escalation for one or both age cohorts may be done for administrative purposes. Detailed plans for data analysis will be documented in the study SAP or in a separate SAP for interim analysis only.

13.12. Other Statistical Issues

Additional analyses may be conducted. Any such analyses will be detailed in the SAP.

14. SPECIAL REQUIREMENTS AND PROCEDURES

14.1. Compliance with Ethical and Regulatory Guidelines

This study will comply with ICH-GCP, with the latest version of the Helsinki declaration and with applicable national regulations, as well as with the European Union Directive 2001/20/EC.

14.2. Institutional and Ethics Review

Before enrollment of patients into the study, the protocol and informed consent (for parents/legal guardians) documents will be reviewed and approved by the appropriate IRB/IEC and regulatory authority. Amendments to the protocol all substantial changes to the trial documentation will be subjected to the same IRB/IEC and regulatory authority review requirements as the original protocol. The Investigator will promptly notify the IRB/IEC and Sponsor of any SAEs or of any other information that might affect the safe use of the IP during the study. IRB approvals/IEC positive opinions and regulatory authorities' approvals must be sent to the Sponsor, or its designee, before initiation of the study or before an amendment is instituted. All correspondence with the IRB/IEC and the regulatory authority should be retained in the study regulatory files.

14.3. Informed Consent and Authorization for Use and Disclosure of Protected Health Information

Written informed consent from each patient, patient's parent(s) or legal guardian(s), must be obtained prior to any study-specific screening evaluations being performed. A copy of the signed informed consent documents will be given to the patient, patient's parent(s) or legal guardian(s); the Investigator will retain the original copies of these documents.

The informed consent documents, as prepared by the Sponsor or designee, must be reviewed and approved by the IRB/IEC and regulatory authorities, as applicable, before initiation of the study. The informed consent document must contain the basic required elements of consent and additional elements, as applicable per regional requirements.

14.4. Compliance with the Protocol

All processes and procedures defined in this protocol will be adhered to. Emergency departures from the protocol that eliminate an apparent immediate hazard to a particular patient and that are deemed by the Investigator as crucial for the safety and wellbeing of that patient may be instituted for that patient only and documented as deviations. The Investigator will contact the Medical Monitor as soon as possible regarding such a deviation. These departures do not require preapproval by the IRB/IEC; however, the IRB/IEC and Medical Monitor must be notified in writing as soon as possible in accordance with the IRB/IEC policies after the departure has been made.

14.5. Confidentiality

14.5.1. Data

All information regarding the nature of the proposed investigation that is provided to the Investigator by the Sponsor, the Sponsor's designee, or the study monitor, with the exception of

information that is required by law or regulations to be disclosed to the IRB/IEC, the patient's parent(s) or legal guardian(s) or the appropriate regulatory authority, must be kept in confidence by the Investigator in accordance with current Health Insurance Portability and Accountability Act (HIPAA) standards and/or European standards.

14.5.2. Patient Confidentiality

The anonymity of participating patients will be maintained to the extent required by applicable laws and in accordance with current HIPAA standards. Patients may be referenced by their initials and an assigned patient identification number on the eCRFs and other data collected by the Sponsor. The Investigator must maintain all documents related to the study that identify the patient (eg, the signed informed consent document) in strict confidence, except to the extent necessary to allow auditing by the appropriate regulatory authorities, the IRB/IEC, the study monitor, or the Sponsor or its representatives.

15. STUDY DOCUMENTATION AND GENERAL INFORMATION

15.1. Essential Study Documents

Essential study documents are among the critical documents required before study enrollment is to occur. Essential documents, as well as supplemental information such as the Investigator's Brochure, Pharmacy Manual, eCRF Completion Guidelines, as specified in the Study Operations Manual and/or regulatory binder, must be kept on-site in a designated study site file.

The study site files will also contain, including but not limited to, patient accountability records, drug accountability (receipt/dispensing) records, Sponsor/Investigator correspondence, IRB/IEC correspondence, deviations, biological sample records, and SAE and Investigational New Drug (IND) safety reports/Safety Alert Letters.

15.2. General Information

The Investigator should refer to the current Investigator's Brochure along with subsequent Safety Alert Letters, the Study Operations Manual, Pharmacy Manual, Laboratory Manual, eCRF Completion Guidelines, and all other study-specific information that is provided during the study initiation visit or by the study monitor.

15.3. Dissemination of Study Results

The information that is developed during the conduct of this clinical study is considered to be strictly confidential. This information may be disclosed only as deemed necessary by Sarepta Therapeutics, Inc. However, at the conclusion of this clinical study, a CSR will be prepared. In addition, a manuscript will be prepared for publication in a reputable scientific journal under the direction of the Sponsor. Sarepta Therapeutics, Inc. will publish and communicate the clinical study results, irrespective of positive or negative findings. Data generated for this study will be exclusively owned by Sarepta Therapeutics, Inc., as detailed in the Clinical Trial Agreement. The study will be registered on the EudraCT database and on ClinicalTrials.gov. After completion of the study, results will be disseminated in accordance with regional requirements.

15.4. Product Handling and Complaints Reporting

If there are any issues during the course of the study related to the quality of the IP, the Investigator, clinical site pharmacist or pharmacy designee should contact the Sponsor or designated CRO.

17. APPENDICES

17.1. Estimated Blood Volumes to be Drawn

World Health Organization (WHO) recommended blood volume limits should be used as a guide for blood sampling in this study (Howie 2011). Per individual, the study-related blood loss should not exceed 3% of the total volume during a 4-week period or 1% of total blood volume within a 24-hour period. Table 6 summarizes the mean blood volume per body weight for children ≤10 kg and Table 7 summarizes the amount of blood required for individual sample collection.

Due to the limitations on the volume of blood collection that is considered to be acceptable in young children with very small total circulating blood volumes, adjustments to sample collection will be made for children weighing <10 kg. These adjustments include the use of 0.5 mL collection tubes for PK samples and utilization of local laboratories for the coagulation panel.

Table 6:	Mean Blood	Volume per	Body Weight
----------	------------	------------	--------------------

Body Weight (kg)	Mean Total Body	Maximum Blood Collection Volume (mL)		
	Blood Volume (mL)	24-Hour Period (1%)	30-Day Period (3%)	
5.0	400	4.0	12.0	
6.0	480	4.8	14.4	
7.0	560	5.6	16.8	
8.0	640	6.4	19.2	
9.0	720	7.2	21.6	
10.0	800	8.0	24.0	

Table 7: Blood Volume Requirements per Test

Test	Volume (mL)	
Chemistry panel	2.0	
Hematology panel	1.0	
Coagulation panela	2.7	
DMD sequencing	2.0	
LTBP4 and SPP-1	2.0	
PK (per sample) ^b	1.0	

DMD = Duchenne muscular dystrophy; LTBP4 = latent transforming growth factor beta binding protein 4; PK = pharmacokinetic; SSP-1 = secreted phosphoprotein 1.

^a Can be done at local laboratory in the event of blood volume limitations

^b 0.5 mL for children weighing < 10.0 kg

Source:

Howie, SR. Blood sample volumes in child health research: review of safe limits. Bull World Health Organ. 2011;89:46-53. doi:10/2471/BLT.10.080010. Available from: http://www.who.int/bulletin/volumes/89/1/10-080010/en/

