2. SCHEDULE OF EVENTS

The schedule of study events is presented in Table 2.

 Table 2:
 Schedule of Events: Screening through Week 48

Study Period Screening Treatment Period: Dose Titration Stable Dos							Dose	se Treatment Period															
Visit/Week	Up to -2 wks	1 BL	2	3	4	5	6	7	8	9	10	11	12	16	18	20	24	28	32	36	40	44	48a
Informed consent ^b	X																						
Inclusion/Exclusion eligibility	X	X																					
Demographics and medical history	X																						
Blood samples genotyping ^b	X																						
Clinical safety laboratory sample ^c	X		X		X				X				X				X			X			X
PK plasma and urine sampling ^d			X				X		X		X						X						
Vital signs ^e	X	X		On weekly infusion days																			
Weight ^f	X	X		Weekly																			
Urine dipstick testing				Weekly																			
Renal function blood tests ^m			X	X	X	X	X	X	X	X	X	X	X	X	X	X	X	X	X	X	X	X	X
Quantitative urine analysis ⁿ			X	X	X	X	X	X	X	X	X	X	X	X	X	X	X	X	X	X	X	X	X
Physical examination (including height/length) ^g	X	X			X				X				X	X		X	X	X	X	X	X	X	X
12-lead ECG ^{i,k}	X								X				X				X			X			X
ECHO ^{i,k}	X								X				X				X			X			X
Eteplirsen dosing ^l					7	Weekl	y IV i	nfusio	n							1	Weekl	y IV i	nfusio	n			

	2 mg/kg	4 mg/kg	10 mg/kg	20 mg/kg	30 mg/kg	30 mg/kg ^l
Concomitant medications					Continuous	S
AE monitoring					Continuous	S

: BL = baseline: DMB = Duchenne muscular

Footnotes for Table 2 Scheduleof Events: Screening through Week 48

Abbreviations: AE = adverse event; dystrophy; DNA = Deoxyribonucleic acid; ECG= electrocardiogram; ECHO = echocardiogram; IV= intravenous; LTBP4= latent transforming growth factor beta binding protein 4;

ent transforming growth factor beta binding protein 4;

PK=pharmacokinetic; SPP-1 = secreted phosphoprotein 1.

- ^a Patients are considered completers for thepurpose of analysis once the Week 48 assessments havebeen completed. Patients may continue in the study up to and including 96 weeks; however, a Safety Follow-up visit will occur approximately 4 weeks after the last doseadministered regardless of the patient's duration in the study (see Table 3).

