- b Patients not previously genotyped may beconsented and havegenotypeperformed as part of the study. Oncethe genotype is con firmed, all additional screening procedures will be performed -2 weeks from Week 1/Baseline. Patients may be enrolled in the study based on historical DNA test results; however, a blood sample for DNA testing will be obtained on all patients to confirm DMD mutation(s). In addition, a second blood sample will be obtained for genotyping of LTBP4 and SPP-1. So that total blood volume taken for the Screening visit does not exceed recommendations, theblood sample for DMD genotyping may be drawn at any time prior to the Week 2 visit and theblood sample for LTBP4 and SPP-1 may be drawn at any timeduring the dose-titration period. If the confirmatory DNA sample is negative for DMD on any enrolled patient, that patient will be withdrawn from the study.
- ^c Clinical safety laboratory assessments (blood chemistry [including liver function], renal function, hematology [including pla telets], and coagulation) must be obtained with results available within 2 weeks prior to dosing. (See Section 10.3.5 for the list of tests to be completed.)
- ^d Pla sma PK samples will be collected pre-dose, immediately prior to the end of infusion (prior to flush) and approximately 1-3 hours and 6-8 hours after completion of study drug infusion. Urine PK will be collected over the first 4 hours after start of infusion.
- ^c Vital signs include blood pressure, heart rate, respiration, and temperature. On infusion days, vital signs will be measured within 60 minutes prior to infusion, within 5 minutes (±2) after the end of infusion, and at 30 minutes (±5), and 60 minutes (±10) after the end of the infusion. All assessments will be performed after patients have remained calm for 5 minutes. Pulse rate and respiratory rate should be measured over 1 minute.
- ^f Weight will be measured prior to study drug infusions at thespecified visits.
- ^g Height/length will be measured as part of every physical examination. The examination will include general appearance; head, ears, eyes, nose, and throat; heart; lungs; chest; abdomen; skin; lymph nodes; musculoskeletal; and neurological systems.
- A 2-week window is allowed in the event the child is unable to complete this assessment at a given visit.
- Only performed in patients 36 months of age and older

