10.3.5. Clinical Safety Laboratory Evaluations

The following routine clinical safety laboratory tests will be collected at the time points specified in Table 2 and Table 3, will be analyzed by an accredited central laboratory selected by the Sponsor, and will be prepared according to the Laboratory Manual provided for the study:

Chemistry: Sodium, chloride, potassium, calcium, glucose, creatinine, blood urea

nitrogen (BUN), albumin, uric acid, total bilirubin, ALP, amylase, ALT, AST, GGT, GLDH, C-reactive protein (CRP), CK, and serum

cystatin C

Hematology: CBC with differential

Coagulation Screen: Prothrombin time, International Normalized Ratio, and activated

partial thromboplastin time

Routine Renal Monitoring

- Quantitative urinalysis: total protein to creatinine ratio (UPCR), urine albumin-to-creatinine ratio (UACR), kidney injury molecule 1 (KIM-1), and urinalysis (pH, specific gravity, protein, glucose, ketones, cytology, hemoglobin
- Renal function blood tests: creatinine, blood urea nitrogen, and cystatin C
- Urine dipstick testing

Persistent, unexplained abnormalities on routine renal blood test monitoring will result in additional renal function tests such as eGFR and 24 hour urine testing for protein.

Any value outside of the current reference ranges for the laboratory performing the test will be flagged on the laboratory results. The Investigator will determine whether abnormal assessment

results are clinically significant or not. Clinical significance is defined as any variation in assessment results that has medical relevance resulting in an alteration in medical care. If clinically significant deterioration from baseline levels is noted, the Investigator will continue to monitor the patient with additional assessments until:

- Values have reached normal range and/or baseline levels; or
- In the judgment of the Investigator together with the Sponsor's Medical Monitor, abnormal values are assessed to be not related to the administration of IP or other protocol-specific procedures, and additional assessments are not medically indicated.

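### Blood draws at Weeks 2, 8 and 24 are not shown to fit the 1% per 24-hour guide: listed volumes total 9.7 mL against 8.0 mL at 10 kg, and below 6.25 kg the reduced volumes exceed 1% before any coagulation draw

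*Protocol*

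**What the plan says.** Protocol Section 17.1 adopts WHO-based limits as a guide: "Per individual, the study-related blood loss should not exceed 3% of the total volume during a 4-week period or 1% of total blood volume" in 24 hours. Table 6 puts the 24-hour maximum at 8.0 mL for a 10.0 kg child. The same section says that "adjustments to sample collection will be made for children weighing <10 kg", and then: "These adjustments include the use of 0.5 mL collection tubes for PK samples and utilization of local laboratories for the coagulation panel".

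Table 7 lists chemistry 2.0 mL, hematology 1.0 mL, coagulation 2.7 mL and PK 1.0 mL per sample. Footnote b reduces the PK sample to "0.5 mL for children weighing < 10.0 kg". Footnote a says of the coagulation panel: "Can be done at local laboratory in the event of blood volume limitations". It sets no weight threshold and gives no local volume.

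In Table 2 (Protocol Section 2) the row "Clinical safety laboratory sample" is marked at Screening and Weeks 2, 4, 8, 12, 24, 36 and 48. Footnote c includes coagulation in that sample. PK sampling is marked at Weeks 2, 6, 8, 10 and 24, and footnote d sets four plasma draws: "PK samples will be collected pre-dose, immediately prior to the end of infusion (prior to flush) and approximately 1-3 hours and 6-8 hours" after the infusion. The two rows coincide at Weeks 2, 8 and 24.

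**The concern.** The small PK tube stops exactly where it is still needed. Between 9.9 and 10.0 kg the daily allowance rises by 0.08 mL, while the PK blood drawn doubles from 2.0 to 4.0 mL. Weight is measured weekly, so a growing child can cross that line during the study. The dilution scheme in Table 5 has a 10 to 15 kg band, so the protocol provides for children of that size.

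Below 10 kg the listed reductions help, but they do not secure the limit for the lightest children, and Table 5 also has rows for 5 to 10 kg and under 5 kg.

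This is research blood from children as young as 6 months. The protocol already uses Section 17.1 to time the genotyping draws (Sections 10.2.3.1 and 10.2.3.2). The visits that combine the panel with the PK series deserve the same check.

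**Working it through.** **Plan's own figure.** Table 6 uses 80 mL/kg: 80 × 10.0 = 800 mL, and 1% is 8.0 mL. All six rows reproduce at both 1% and 3%. The 24-hour limit is therefore 0.8 mL/kg.

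**Assumptions.**
- The panel and the PK series at a visit fall within 24 hours.
- The renal blood tests share the chemistry tube. Section 10.3.5 lists "Renal function blood tests: creatinine, blood urea nitrogen, and cystatin C", and its chemistry panel already contains all three. Table 7 has no separate row for them; a separate tube would raise every total below.
- 80 mL/kg holds above 10 kg, where Table 6 stops.

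**Volumes at Weeks 2, 8 and 24.**
- 10 kg and above, as listed: 2.0 + 1.0 + 2.7 + 4 × 1.0 = 9.7 mL. At 10.0 kg, 9.7/800 = 1.21%, which is 1.7 mL over.
- The same without the central coagulation tube: 9.7 − 2.7 = 7.0 mL (0.875% at 10.0 kg).
- Below 10 kg, before coagulation: 2.0 + 1.0 + 4 × 0.5 = 5.0 mL. With the full 2.7 mL tube: 7.7 mL.

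| Weight (kg) | 1% limit (mL) | Total before coagulation (mL) | Room for coagulation (mL) | Total with 2.7 mL tube (mL) |
|---|---|---|---|---|
| 5.0 | 4.0 | 5.0 | −1.0 | 7.7 |
| 6.0 | 4.8 | 5.0 | −0.2 | 7.7 |
| 6.25 | 5.0 | 5.0 | 0 | 7.7 |
| 7.0 | 5.6 | 5.0 | 0.6 | 7.7 |
| 7.5 | 6.0 | 5.0 | 1.0 | 7.7 |
| 9.9 | 7.92 | 5.0 | 2.92 | 7.7 |
| 10.0 | 8.0 | 7.0 | 1.0 | 9.7 |
| 11.0 | 8.8 | 7.0 | 1.8 | 9.7 |
| 12.0 | 9.6 | 7.0 | 2.6 | 9.7 |
| 12.5 | 10.0 | 7.0 | 3.0 | 9.7 |

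**Break points.**
- The listed 9.7 mL fits from 9.7/0.8 = 12.1 kg.
- With 0.5 mL PK tubes, the full coagulation tube fits from 7.7/0.8 = 9.6 kg.
- The 5.0 mL before coagulation fits from 5.0/0.8 = 6.25 kg. Above that, and below 10 kg, the room for coagulation is 0.8 × weight − 5.0 mL.

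**4-week limit at 10.0 kg.** The heaviest 4-week span, for example Weeks 2, 4 and 6, takes 9.7 + 5.7 + 4.0 = 19.4 mL against 24.0 mL.

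**The case against.** The best reply is that Section 17.1 already contains the remedy. Footnote a applies at any weight whenever blood volume is limiting, and a 10 kg child is such a case. The 9.7 mL is the total with that remedy unused; with it, the known total is 7.0 mL. The local volume may stand in the Laboratory Manual, which is not among the documents. The limit is a guide, Table 2 schedules by week, and nothing requires the panel and the PK series within the same 24 hours.

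Most of this stands. A reader might infer that the protocol breaches its own limit at 10 kg. The documents do not support that: a local draw of up to 1.0 mL keeps within it. A reader might also infer a breach of the 3% limit or an error in Table 6. Neither is there: the 4-week total at 10.0 kg is 19.4 mL against 24.0 mL, and Table 6 is correct.

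The reply does not dispose of the point. Footnote a is permissive and gives no volume, so compliance cannot be shown from the protocol. Nor does it help below 6.25 kg, where the excess arises before coagulation. Between 6.25 and 7.5 kg the room for the local draw is smaller than at 10 kg. The protocol does not forbid separate days, but does not provide for them either.

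**Conclusion.** The point holds as a gap in the blood-volume plan that should be closed, in two parts.

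- **10 to about 12.1 kg:** the listed volumes exceed the 1% guide by 1.7 mL at 10 kg, 0.9 mL at 11 kg and 0.1 mL at 12 kg. With local coagulation an excess is possible, not certain: it arises only if the local draw is more than 1.0, 1.8 or 2.6 mL respectively.
- **Below 10 kg:** the reduced volumes exceed 1% below 6.25 kg whatever the coagulation volume. From 6.25 to about 9.6 kg, compliance depends on an unstated local volume, most tightly at the lower end.

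Both parts rest on draws within 24 hours and a shared chemistry and renal tube. The upper bound of 12.1 kg also rests on extending 80 mL/kg. The amounts are modest, the limit is a guide, and the documents do not say how many children fall in either range.

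**What to change.** 1. In Section 17.1 and Table 7 footnote b, raise the 0.5 mL PK tube cut-off from <10 kg to at least <12.5 kg. The 10 kg total becomes 7.7 mL (0.96%), even with the full central coagulation tube. At 12.5 kg the 9.7 mL total needs a blood volume of at least 9.7/0.125 = 77.6 mL/kg. A 15 kg cut-off holds down to 9.7/0.15 = 64.7 mL/kg, but is an optional margin.
2. Below about 9.6 kg, take the coagulation sample at an adjacent weekly infusion visit unless the local draw is at most 0.8 × weight − 5.0 mL.
3. Below 6.25 kg, take the whole safety panel, with its renal tests, on a different day from the PK series. The PK day is then 2.0 mL and the panel day 3.0 mL plus the local draw, which leaves 1.8 mL for it at 6 kg and 1.0 mL at 5 kg. An adjacent weekly visit avoids an extra trip; none of the weeks next to 2, 8 and 24 has a PK series.

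The cost is an edit to Section 17.1, footnote b and the Laboratory Manual. The small tube is already in the study. The downside is less plasma for PK retest in children of 10 to 12.5 kg, and some safety or coagulation samples about a week away from the PK visit. Moved samples should be entered on the scheduled visit's eCRF page: SAP Section 5.6 assigns time points by page and leaves unscheduled safety assessments out of the by-visit summaries.
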